7.9 Efficacy Analysis

The analyses and summaries for efficacy will be based on the FAS, unless otherwise noted.

7.9.1 **Primary Efficacy Endpoint(s)**

The primary endpoint is the change from Baseline on the PANSS NSFS at Day 84. The details of PANSS NSFS calculation can be found in Section 7.9.4.

The primary endpoint will be analyzed by comparing TAK-831 and placebo over all assessed time points using estimates from a mixed model for repeated measures (MMRM) with Baseline value as a covariate; pooled site, visit, treatment, and categorical age (randomization factor) as fixed factors; and treatment-by-visit and Baseline-by-visit interactions. Based on a Missing at Random Assumption, this analysis will be performed using observed case data only. The effect at each time point for each treatment is allowed to vary freely and an unstructured covariance matrix is assumed. If the model does not converge, other covariance structures (unstructured, compound symmetry, 2-Toeplitz, etc) will be considered.

Multiplicity will be controlled across dose-arms by first testing the 125 mg QD and 500 mg QD dose-arms in parallel using Holm's method to control the overall type I error rate at the 0.10 level (one-sided), then testing the 50 mg QD dose-arm at the 0.10 level if at least 1 of other doses is found to be statistically superior to placebo.

In order to provide additional insight about dose-response, the primary endpoint may be analyzed using a Multiple Comparison Procedure-Modeling (MCP-Mod) approach (Pinheiro et al, 2014).

For MCP-Mod approach, DoseFinding package in R statistical analysis software will be used. R has been validated by the contract research organization for this study. The following set of models will be fit to detect a dose response: linear, E_{max} , quadratic, and exponential. The stratification factor of age (<35 and \geq 35 years) will be included in the models. Each of the dose-response shapes in these models will be evaluated using optimal contrasts and applying MCP-Mod techniques to preserve the family-wise error rate (FWER) with the overall 1-sided significance level of 0.10. The effective dose(s) will be determined within this framework. The stratification factor of age may be omitted if the dose response for the stratified models cannot be reliably estimated.

The following supplementary analyses will also be conducted for the primary endpoint:

- 1) A method for missing value imputation based on pattern mixture models (PMM) using standard SAS STAT procedures. It is assumed that after discontinuation from the study, subjects receiving a TAK-831 dose will exhibit the same future evolution of the disease as subjects on the placebo treatment. The missing PANSS NSFS scores in the TAK-831 dose arm will be imputed using placebo-based pattern mixture models. This method uses sequential regression and multiple imputation methodology to impute missing values for visits after a subject's discontinuation from the study in the placebo arm. Then based on the available data from placebo subjects, the missing values for mactive treatment arm will be imputed using pattern mixture models until missing values at all visits are imputed.
- 2) The primary endpoint also be analyzed using analysis of covariance (ANCOVA), with pooled center, stratification factor, and treatment as fixed factors, and PANSS NSFS Baseline score as a covariate. ANCOVA based on the multiply-imputed data will be performed.

As a supportive analysis, the primary endpoint will be analyzed using MMRM in the same manner as described in section 7.9.1, but based on the PPS.

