13.1.3 Efficacy Analysis

13.1.3.1 Analysis of Primary Efficacy Endpoint

The primary endpoint will be analyzed by comparing TAK-831 and placebo over all assessed time points using estimates from a mixed model for repeated measures (MMRM) with baseline value as a covariate; pooled site, visit, treatment, and categorical age (randomization factor) as

fixed factors; and treatment-by-visit and baseline-by-visit interactions. Based on a Missing at Random Assumption, this analysis will be performed using observed case data only. The effect at each time point for each treatment is allowed to vary freely and an unstructured covariance matrix is assumed. If the model does not converge, other covariance structures (unstructured, compound symmetry, 2-Toeplitz, etc) will be considered.

Additional analyses to address sensitivity to missing data will be specified in the SAP.

Multiplicity will be controlled across dose-arms by first testing the 125 mg QD and 500 mg QD dose-arms in parallel using Holm's method to control the overall type I error rate at the 0.10 level (one-sided), then testing the 50 mg QD dose-arm at the 0.10 level if at least 1 of other doses is found to be statistically superior to placebo.

In order to provide additional insight about dose-response, the primary endpoint may be analyzed using a Multiple Comparison Procedure-Modeling (MCP-Mod) approach. Additional details of the MCP-Mod analysis will be specified in the SAP.

Before unblinding the data, the team will assess the degree of impact from COVID-19 on PANSS NSFS data completeness or collection modality. If the impact is deemed minimal, which is defined as less than 5% of the enrolled subjects having remote or missing final assessments due to COVID-19, then the original analysis plan will be followed. If there is more than a minimal impact, then a more thorough blinded review will be performed. After the blinded assessment, if substantial changes to the statistical analyses are needed to address the impact, the SAP will be amended before study unblinding. Minor changes may be documented in the clinical study report.

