Appendix A Schedule of Study Procedures

	Screening	Placebo Run-in	12-Week Double-Blind Treatment Period					Safety Follow- up			
Study Day	Days -42 to -15 ^a	Day -14	Day 1 b	Day 7 q	Day 14 ^q	Day 28 q	Day 42 q	Day 56 q	Day 70 q	Day 84/ ET b, c	Days 94- 98 (10-14 days after last dose)
Visit Number	1	2	3	4	5	6	7	8	9	10	11
Visit Window (Days) d		+7 e	±2	±2	±1	±2	±2	±2	±2	±5	±2
Informed consent	X										
Clinical Trial Subject Database consent	X										
Informant informed consent f	X	X									
MINI	X										
Centralized subject eligibility assessment	X	X									
Inclusion/exclusion criteria	X	X	X								
Demographics, medical history, substance use	X										
Medication history	X										
Concurrent medical conditions	X										
Physical examination	X									X	
Vital signs ^g	X	X	X	X	X	X	X	X	X	X	X
Height, BMI, weight h	X									X	
Concomitant medications	X	X	X	X	X	X	X	X	X	X	X
Clinical laboratory tests ¹	X		X			X		X		X	
HBsAg, anti-HCV	X										
FSH	X										
HbA1c	X										
Pregnancy test (hCG) ¹	X	X	X			X		X		X	X
Urine drug screen k	X	X	X			X		X		X	
12-lead ECG	X		X							X	
C-SSRS	X	X	X	X	X	X	X	X	X	X	X
CDSS	X										
Modified SAS	X										
PANSS	X	X	X			X		X		X	
BNSS	X	X	X			X		X		X	
CGI-SCH-I						X		X		X	
CGI-SCH-S	X	X	X			X		X		X	
BACS ^T		X	X				X			X	

	Screening	Placebo Run-in	12-Week Double-Blind Treatment Period				Safety Follow- up				
Study Day	Days -42 to -15 ^a	Day -14	Day 1 b	Day 7 q	Day 14 ^q	Day 28 ^q	Day 42 ^q	Day 56 q	Day 70 q	Day 84/ ET b, c	Days 94- 98 (10-14 days after last dose)
Visit Number	1	2	3	4	5	6	7	8	9	10	11
Visit Window (Days) d		+7 e	±2	±2	±1	±2	±2	±2	±2	±5	±2
SCoRS			X							X	
Plasma sample for TAK-831 PK ⁿ			X			X	X	X		X	
Plasma sample for PD (D- and L-serine) ⁿ		X	X			X	X	X		X	
Plasma sample for antipsychotic medications	X	X					X			X	
PTE/AE assessment	X	X	X	X	X	X	X	X	X	X	X
Call IRT for subject ID/medication ID		X	X	X	X	X	X	X	X	X	
Digital compliance technology training		X									
Randomization			X								
Dispense study drug ^p		X	X	X	X	X	X	X	X		
Study drug return/accountability/complian ce			X	X	X	X	X	X	X	X	
In-clinic study drug dosing		X	X			X					

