During the Screening Period (Days -42 to -15), subjects will visit the clinic and receive full medical, neurological, and psychiatric examinations as well as be familiarized with study procedures. Additional screening procedures include diagnostic assessments, safety assessments, and other clinical assessments. An adult informant capable of providing information about the subject's symptoms and function for the PANSS and SCoRS must attend the Screening or Placebo Run-in Visit for evaluation by site staff and to provide written informed consent for informant study participation. Alternatively, a site staff member may also go to the informant's location to obtain informed consent and, if a qualified rater, obtain the informant interview; or the informant interview may be conducted by phone if the site staff is not a rater. If the informant is unavailable for an in-person interview at the screening visit, the initial informed consent may be obtained in a telephone discussion (as permitted by local ethics and regulatory policy) so that the informant information may be included in the screening assessments requiring informant input.

Subject eligibility for the study will be confirmed by a centralized vendor that will also provide rater qualification, training, and ongoing rater quality monitoring throughout the conduct of the study. For the Screening Visit, the centralized vendor will review documentation and recordings of the diagnostic and selected symptom assessment interviews as well as collected information addressing key study entry criteria. The study site must receive documentation of approval of subject eligibility before the subject can be enrolled into the Single-Blind Run-in Period.

The 2-week Single-Blind Placebo Run-in Period (Days -14 to -1) will be used to evaluate compliance with study drug intake and stability of BNSS and PANSS scores. During this period, all subjects will receive placebo tablets that appear identical to the study drug to be used during the randomized Double-Blind Treatment Period. Note: If the scheduling of the Day 1 visit is delayed for any reason, the subject should be instructed to continue treatment with run-in medication until the Day 1 visit is reschedule.

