5.0 ANALYSIS ENDPOINTS

Baseline is defined as the assessment prior to dosing on Day 1 for all assessments other than the where Baseline is defined as the Day -14 assessment.

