7.0 METHODS OF ANALYSIS AND PRESENTATION

7.1 General Principles

Baseline values are defined as the last observed value before the first dose of study medication.

All statistical analyses will be conducted using SAS[®] Version 9.4, or higher, unless otherwise noted.

All confidence intervals, statistical tests, and resulting P-values will be reported as 2-sided and will be assessed at α =0.05 significance level unless otherwise stated. P-values will be rounded to 3 decimal places prior to assessment of statistical significance.

Means and medians will be presented to 1 more decimal place than the recorded data. The standard deviations (SDs) will be presented to 2 more decimal places than the recorded data. Confidence intervals about a parameter estimate will be presented using the same number of decimal places as the parameter estimate.

Where appropriate, variables will be summarized descriptively by study visit. For the categorical variables, the count and proportions of each possible value will be tabulated by treatment group. The denominator for the proportion will be based on the number of subjects who provided non-missing responses to the categorical variable. For continuous variables, the number of subjects with non-missing values, mean, median, SD, minimum, and maximum values will be tabulated.

Screen failure subjects will be grouped and listed at the end.

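### The primary MMRM and the ANCOVA adjust for the Day 1 PANSS NSFS only; the scheduled Day -14 rating is a second pre-randomization covariate that could add some precision at almost no cost

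*SAP*

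**What the plan says.** The primary endpoint is the change in PANSS NSFS from baseline to Day 84. SAP 7.9.1 specifies the model as "MMRM) with Baseline value as a covariate; pooled site, visit, treatment, and categorical age (randomization factor) as fixed factors", with treatment-by-visit and baseline-by-visit interactions. Protocol 13.1.3.1 gives the same covariate set: "mixed model for repeated measures (MMRM) with baseline value as a covariate".

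Baseline is one value. SAP 5.0 says "Baseline is defined as the assessment prior to dosing on Day 1" (one assessment, whose name is redacted, uses Day -14 instead). SAP 7.1 says "Baseline values are defined as the last observed value before the first dose of study medication". Neither averages earlier ratings. The supplementary ANCOVA in SAP 7.9.1 adjusts for the same single score, and the per-protocol analysis repeats the same MMRM.

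The schedule in Protocol Appendix A places PANSS at screening, Day -14 and Day 1, all before the first double-blind dose, and then at Days 28, 56 and 84. SAP 4.4 gives the run-in a use for these scores: it "will be used to evaluate compliance with study drug intake and stability of BNSS and PANSS scores". The numerical stability rule for entry (Protocol 7.1, criterion 10) is on the BNSS total only.

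**The concern.** A single clinician rating measures the subject's underlying level with rater and day-to-day error. A second rating of the same score two weeks earlier can measure that level better and so explain more of the Day 84 variance. It is taken before randomization, so treatment cannot affect it and adjusting for it does not bias the dose comparisons. The endpoint, the estimand, the alpha level and the Holm procedure stay as they are.

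The rating is already scheduled and paid for. Protocol 9.1.10.2 puts a PANSS at about 45 minutes and has it recorded for outside review. What is at stake is some precision in the three dose comparisons, in a study whose recomputed power lies just above its stated minimum and already relies on 85% completion.

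**Working it through.** **Inputs from the documents.**
- Randomized: 52 per dose and 78 on placebo (Protocol 2.0).
- Completion 85%; effect size 0.4 for 125 mg and 500 mg; power at least 82% for at least one dose (Protocol 13.3, SAP 6.0).
- Holm across these two doses at 0.10 one-sided (SAP 7.9.1), so the first step tests each at 0.05 one-sided, critical value 1.645.

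**Step 1: reproduce the stated power.**
- Completers: 0.85 × 52 = 44.2 per dose; 0.85 × 78 = 66.3 on placebo.
- Standard error in SD units: sqrt(1/44.2 + 1/66.3) = 0.1942.
- Mean of each test statistic: 0.4/0.1942 = 2.06.
- Correlation of the two contrasts through the shared placebo arm: (1/66.3)/(1/44.2 + 1/66.3) = 0.40.
- Power for at least one dose: 1 − P(Z1 < 1.645 and Z2 < 1.645), bivariate normal, = **82.8%**. This agrees with at least 82%.

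**Step 2: effect of a second covariate.** Let a = corr(Day -14, Day 1), b = corr(Day 1, Day 84) and c = corr(Day -14, Day 84). Relative to Day 1 alone, adding Day -14 lowers the residual variance of Day 84 by the fraction

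f = (c − ab)² / [(1 − a²)(1 − b²)].

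If 0.4 is standardized to the SD after Day 1 adjustment, the effect size becomes 0.4/sqrt(1 − f), and Step 1 is repeated with it. When c = ab, Day -14 says nothing about Day 84 beyond Day 1, and f = 0.

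Example, a = 0.85, b = 0.60, c = 0.60: f = (0.60 − 0.51)²/(0.2775 × 0.64) = 0.0081/0.1776 = 4.6%; effect size 0.409; power 84.2%.

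**Step 3: range.** The documents give none of a, b or c, so every row is an assumption. b is held at 0.60.

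| a | c | Variance reduction | Power | Gain (points) |
|---|---|---|---|---|
| 0.90 | 0.54 (= ab) | 0 | 82.8% | 0 |
| 0.90 | 0.55 | 0.1% | 82.9% | 0.0 |
| 0.90 | 0.58 | 1.3% | 83.2% | 0.4 |
| 0.90 | 0.60 | 3.0% | 83.7% | 0.9 |
| 0.85 | 0.55 | 0.9% | 83.1% | 0.3 |
| 0.85 | 0.57 | 2.0% | 83.4% | 0.6 |
| 0.85 | 0.60 | 4.6% | 84.2% | 1.4 |
| 0.80 | 0.48 (= ab) | 0 | 82.8% | 0 |
| 0.80 | 0.58 | 4.3% | 84.1% | 1.3 |
| 0.80 | 0.60 | 6.3% | 84.7% | 1.9 |
| 0.75 | 0.60 | 8.0% | 85.3% | 2.4 |
| 0.60 | 0.60 | 14.1% | 87.1% | 4.3 |

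The cost is one extra slope per visit, negligible against about 199 completers (0.85 × 234).

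**The case against.** The strongest reply is that nothing is wrong. Adjusting for the predose baseline and its interaction with visit is a valid model, the protocol and SAP state it consistently, and the planned power is met. That stands, and it is why this point is about efficiency only.

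The second reply is that the gain may be close to nothing. Subjects enter on stable symptoms and stable medication, and with BNSS totals at Day -14 and Day 1 within 20% of screening. Two ratings 14 days apart in such subjects may correlate at 0.85 to 0.90, which makes the second largely redundant. This also stands. A reader might infer that power is certainly being lost, or that the change is worth about 16% more subjects (1/(1 − 0.141) = 1.16). The documents support neither. The first needs correlations that they do not report. The second needs pre-treatment ratings two weeks apart to agree no better than ratings twelve weeks apart.

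A reader might also carry the same gain over to BNSS and BACS, because SAP 7.9.2 analyses other continuous endpoints in the same manner. That does not follow. The entry rule selects directly on BNSS stability, so its two pre-randomization totals are held close and the gain may be smaller. BACS is a performance test with its own schedule and its own, unreported, correlations.

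Finally, this is more than a one-sentence SAP edit, because Protocol 13.1.3.1 names the same covariates.

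**Conclusion.** The point holds as an optional improvement that is valid and nearly free. A Day -14 PANSS is scheduled for every subject before randomization (scheduled, so some values may be missing), and it enters no visible efficacy model.

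The likely size is modest: about 0 to 1.5 points of power with a Day -14/Day 1 correlation of 0.85 to 0.90, 0 to about 2.5 points at 0.75 to 0.80, and about 4 points only in the optimistic case of equal correlations of 0.6. It is zero if Day -14 adds nothing once Day 1 is known. These figures rest on two assumptions that the documents do not settle: that 0.4 is relative to the SD after Day 1 adjustment, and that Day 1 and Day 84 correlate at 0.60.

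The plan should not be read as biased, inconsistent or short of its stated power on this account.

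**What to change.** Before unblinding:

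1. In SAP 7.9.1, add the Day -14 PANSS NSFS and its interaction with visit to the primary MMRM as a second covariate. The per-protocol MMRM inherits this.
2. Add Day -14 NSFS to the supplementary ANCOVA and, since that analysis uses multiply imputed data, to the imputation model.
3. Keep Day 1 as the reference for change from baseline.
4. State a rule for missing Day -14 values that uses pre-randomization data only, for example the overall Day -14 mean.
5. Record the change against Protocol 13.1.3.1, which lists the present covariates.

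The correlations can first be checked on blinded pooled data. If they show that Day -14 adds nothing beyond Day 1, a sentence giving that reason for keeping the present model is enough. The same covariate may be added for BNSS and BACS, both scheduled at Day -14 and Day 1, but without claiming a particular gain.

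The cost is a short SAP amendment, a note of the departure from the protocol text and one slope per visit. No new data are needed.

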Permuted block randomization will be used. The randomization will be stratified by age at Screening (<35 and ≥35 years of age). The allocation ratio will be 2:2:2:3 to the 3 TAK-831 arms and placebo arm respectively.

A schematic of the study design is included as Figure 4.a.

Figure 4.a Schematic of Study Design

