6.0 DETERMINATION OF SAMPLE SIZE

Assuming that the effect size is at least 0.4 for the as 125 mg QD and 500 mg QD doses and that at least 85% of the 234 subjects complete the Day 84 assessment, the study has at least 82% power for at least 1 dose to be statistically significant at the 0.10 level with correction for multiple doses.

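### Optional efficiency gain: step-down Dunnett in place of Holm for the 125 mg and 500 mg tests would add about 1.4 points of power at the same pairwise error rate, provided the 50 mg rule is corrected with it

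*SAP*

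**What the plan says.** SAP 7.9.1 controls multiplicity across doses by "testing the 125 mg QD and 500 mg QD dose-arms in parallel using Holm's method to control the overall type I error rate"; the level is one-sided 0.10. The third dose follows: "then testing the 50 mg QD dose-arm at the 0.10 level if at least 1 of other doses is found to be statistically superior to" the control arm. Protocol 13.1.3.1 and the protocol synopsis (Section 2.0, Primary Efficacy Analysis) give the same rule.

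The sample size section, SAP 6.0, claims that "the study has at least 82% power for at least 1 dose to be statistically significant at the 0.10 level", after correction for multiple doses. It assumes an effect size of at least 0.4 for 125 mg and for 500 mg and that "at least 85% of the 234 subjects complete the Day 84 assessment". Protocol 13.3 and the synopsis say the same.

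On allocation, SAP 4.4 says: "The allocation ratio will be 2:2:2:3 to the 3 TAK-831 arms and placebo arm respectively". The synopsis gives 52 subjects per dose arm and 78 on placebo.

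Neither document mentions the correlation that the shared placebo arm creates, or a Dunnett-type adjustment for these pairwise tests.

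**The concern.** Holm compares the smaller of the two p-values with half of 0.10. That threshold protects against any dependence between the tests, including the worst. Here the dependence is known from the design: the two comparisons share a placebo arm, so they are positively correlated and tend to reject together. When neither dose works, the chance of at least one false rejection is then below the 0.10 that the sponsor accepted. A test that uses the known correlation can set a slightly easier first threshold and still keep the pair at 0.10. What is at stake is a little power on the criterion by which the trial was sized, namely a win on at least one of the two higher doses.

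**Working it through.** **Inputs.** 52 subjects per dose and 78 on placebo (protocol synopsis); 85% completion and effect size 0.4 (SAP 6.0); overall one-sided 0.10 with Holm (SAP 7.9.1). Assumptions: equal variances, equal completion in every arm, and a normal approximation to the MMRM Day 84 contrasts.

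**Step 1. The plan's own power figure.**
- Completers: 52 × 0.85 = 44.2 per dose; 78 × 0.85 = 66.3 on placebo.
- Standard error in SD units: √(1/44.2 + 1/66.3) = 0.1942. Mean of each test statistic: 0.4/0.1942 = 2.060.
- Correlation of the two contrasts: (1/66.3)/(1/44.2 + 1/66.3) = 0.40.
- Holm's first step uses one-sided 0.05, critical value 1.645. Power for a single dose at that level is 66.1%.
- Power for at least one dose = 1 − P(Z₁ < 1.645, Z₂ < 1.645), bivariate normal with means 2.060 and correlation 0.40, = **82.8%**. This matches the stated figure. Treating the tests as independent would give 88.5%.

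**Step 2. Error spent by Holm's first step.** With both means at zero, 1 − P(Z₁ < 1.645, Z₂ < 1.645) = **0.0906**. This holds only when neither dose works. If one dose works strongly, it is rejected almost surely, the other is tested at the full 0.10, and the pair's simulated error is 0.100 under Holm and under step-down Dunnett alike.

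**Step 3. Step-down Dunnett for the pair.** Solve P(Z₁ < c, Z₂ < c) = 0.90 at correlation 0.40: c = **1.594**, one-sided 0.0555. If the larger statistic passes, the other dose is tested at one-sided 0.10, as under Holm.

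| Quantity (effect 0.4, 85% completion) | Holm | Step-down Dunnett |
|---|---|---|
| Pair's error, neither dose works | 0.091 | 0.100 |
| Power, at least one dose, both work | 82.8% | 84.3% |
| Power, both doses, both work | 63.3% | 63.8% |
| Power, at least one dose, only one works | 66.5% | 68.4% |

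The gain for at least one dose is 82.84% to 84.27%, or 1.43 points before rounding.

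**Step 4. Sensitivity of the gain.**
- Whole-number completers (44 and 66): 82.7% to 84.1%, 1.44 points.
- t distribution with 194 df: critical values 1.653 and 1.600; 82.6% to 84.1%, 1.5 points.
- All 234 completing: 87.4% to 88.5%, 1.2 points.
- Effect size 0.3: 64.4% to 66.5%, 2.1 points. Effect size 0.5: 93.7% to 94.4%, 0.7 point.

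**Step 5. Effect on the whole three-dose procedure.** The pair is also the gate to 50 mg. Simulated chance of at least one false rejection over the three doses (4 million draws, correlation 0.40 throughout):

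| Truth | Holm | Step-down Dunnett |
|---|---|---|
| No dose works | 0.090 | 0.100 |
| One high dose works at effect 0.4, other two doses do not | 0.156 | 0.158 |
| One high dose works strongly, other two doses do not | 0.173 | 0.173 |

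**The case against.** The strongest reply is that nothing is wrong. Holm is valid under any dependence and needs only the two p-values. The trial was sized with it, and the stated power is correct for it. The gain is small, and ordinary uncertainty about dropout outweighs it: moving completion from 80% to 90% shifts Holm's power from 81.0% to 84.5%. All of this stands, and it is why the point is an optional improvement.

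A second reply is that the change loosens the gate to 50 mg in a procedure whose three-dose error already exceeds 0.10 when only one high dose works. This also stands. The increase is small (0.156 to 0.158 at effect 0.4), but it goes the wrong way, and the gate matters more than 1.4 points of power.

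Three stronger readings are tempting, and the documents do not support them:
- A reader might infer that the stated power is wrong, or was computed without the shared placebo. The 82% is reproduced only when the 0.40 correlation is included.
- A reader might infer that the pair always underspends its error. The 0.091 applies only when neither dose works.
- A reader might infer that the whole testing scheme is conservative. The slack belongs to the first step of the pair alone, and Step 5 shows the three-dose error above 0.10.

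The reply that this is mere preference does not fully hold. Step-down Dunnett rejects whenever Holm rejects, because its first threshold is easier and its second is the same. It also keeps the pair at one-sided 0.10, so within the pair no power is lost.

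**Conclusion.** This is a cheap improvement and corrects no error. With the plan's own inputs, Holm's first step spends about 0.091 of the one-sided 0.10 when neither higher dose works. Using the known correlation of 0.40 would add about 1.4 points of power for at least one dose and about 0.5 point for both.

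The size depends on effect size 0.4, equal 85% completion, equal variances and approximate joint normality of the two MMRM contrasts. It is nearer 2 points at effect size 0.3 and under 1 point at 0.5. The priority is low, and the change is worth making only alongside a correction of the 50 mg rule.

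**What to change.** Before unblinding, in SAP 7.9.1:
- Replace Holm by the step-down Dunnett test for the 125 mg and 500 mg pair. Compare the larger Day 84 statistic with the Dunnett critical value computed from the MMRM-estimated covariance of the two contrasts (about 1.594 under the planned allocation). If it passes, test the other dose at one-sided 0.10.
- State the degrees-of-freedom rule for that critical value.
- Correct the 50 mg rule in the same edit, so that the multiplicity scheme is settled as a whole.
- Record the departure from the Holm wording in the protocol synopsis and Protocol 13.1.3.1, and review the power statements in SAP 6.0, Protocol 13.3 and the synopsis.

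**Cost.** A short SAP amendment with a recorded justification, and a multivariate critical value in the analysis program. The covariance comes from the MMRM fit that is already planned. The one added assumption is joint normality of the two contrasts. Protocol 13.1 requires the SAP to be final before the study team is unblinded; after that point Holm should stay. If the sponsor prefers to keep Holm, no stated figure needs to change.
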